The randomized sequence will be generated by using the Web site Randomization.com (<http://www.randomization.com>) using the Random Block Size method for 24 subjects in two groups. The sequence will be stored electronically in a password-protected document.

The Research Coordinator 1 is assigned to:

- Manage the randomized sequence electronic file.
- Assign participants to subgroups according to the randomized sequences.

c. HIPAA Compliance

As per the Local IRB of Record Consent Form Template, the HIPAA compliance/authorization language is included in the Consent Form.

d. Pregnancy:

As per the local IRB of Record, pregnant participants are typically excluded from protocols using ionizing radiation. Also, while there are no known risks to an embryo or fetus associated with FES during pregnancy, this research may hurt an embryo or fetus in ways we do not currently know. For this reason, pregnant women cannot take part in this study. If a woman is capable of having children, she must have a pregnancy test. The pregnancy test will be performed during the post-consent screening. If the subject becomes pregnant (or suspect pregnancy) before this study is completed, the subject must inform the study team immediately.

XI. DATA COLLECTION and ANALYSIS

a. Study Procedures

1. Study design, including the sequence and timing of study procedures (distinguish research procedures from those that are part of routine care).

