n) Pain and Spasticity Medication inventory: This is a routine exam performed for people with spinal cord injury. Pain and antispasticity medications dose will recorded.

o) FES Evaluation: This is a routine exam performed for people with spinal cord injury prior to receiving FES. Therapist 1 or 6 will test the different muscles that are targeted for this study to achieve the best motor response to FES, and maintain subject comfort. Depending on the neurological level of the subject, the muscles are: supraspinatus; infraspinatus; teres major and minor; anterior, middle, or posterior deltoid; biceps; and triceps.

(2) Intervention:

The subjects will be randomly assigned, in a one-to-one ratio, either to group 1, which will first engage in the FES assisted ergometry followed by the non-FES assisted exercise, or to group 2, which will first engage in the non-FES assisted exercise followed by the FES assisted ergometry.

p) FES Upper Extremity Cycle Ergometry: While undergoing the FES assisted ergometry intervention, the subjects will use an RT300-SLSA upper extremity ergometer configured with FES. Electrode placement will be individually optimized to produce smooth cycling, as measured by crank symmetry, average stimulation level, expended energy per hour, and muscle stiffness. Parameters of stimulation current will also be individually optimized to achieve the best motor response (frequency of 10 to 100 Hz, pulse duration of 50 to 500 μ s, and amplitude of 10 to 140 mA). Silver mesh self-adhesive surface electrodes will be used to conduct the stimulation. They will activate some combination of the following muscles, depending on the neurological level at which they are applied: supraspinatus; infraspinatus; teres major and minor; anterior, middle, or

posterior deltoid; biceps; and triceps. Target cycling speed will be 20 rpm, with a resistance of 0.965Nm. The subjects will warm up between 2 and 10 minutes depending on muscle stiffness or spasms, actively cycle with FES for 1 hour, and cool down of 2 minutes. The ergometer software will be set to provide motor support once muscle fatigue has been reached so the subjects can continue. The subjects will remain seated in their primary wheelchair throughout the treatment. The subjects will cycle for 60 minutes/session, three times a week for 4 months.

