q) Non-FES Upper Extremity Exercise: While undergoing the non-FES exercise intervention, the subjects will receive a specific, individualized exercise regimen, consisting of strengthening, stretching, splinting and any other therapeutic interventions that do not use electrical stimulation.. The subjects will remain seated in their primary wheelchair throughout the treatment. The subjects will exercise for 60 minutes/session, three times a week for 4 months.

2. Study duration and number of study visits required of research participants.

The study will last 12 months. The Study Time Line is found in Figure 1, and the Data Collection Schedule in Table 1.

(1) Assessment:

The following post-consent screening will be performed at the Initial visit:

- a. Neurological Exam (about 30 minutes)
- b. Fast Urine Pregnancy Test (about 15 minutes)

The following assessments will be performed at the Initial Visit:

- o. FES Evaluation (about 15 minutes)

The following assessments will be performed at the Initial, 4th month, 9th month, and 12th month Visits:

- c. Severity of gleno-humeral subluxation (about 30 minutes)

The following assessments will be performed at the Initial, 4th month, 5th month, 9th month, and 12th month Visits:

- d. Spasticity measurement (about 15 minutes)
- e. Capabilities of the Upper Extremity test (about 10 minutes)
- f. Jebsen-Taylor Hand Function test (about 15 minutes)
- g. Box and Blocks test (about 15 minutes)
- h. Action Research Arm test (about 20 minutes)
- i. Functional Reach test (about 5 minutes)
- j. Range Of Motion of the upper extremity joints (about 30 minutes)
- k. Numerical Rating Scale (NRS) for pain (about 1 minutes)
- l. Pulmonary Function Test (PFTs) (about 5 minutes)
- m. American Spinal Injury Association (ASIA) exam (about 60 minutes)
- n. Pain and Spasticity Medication inventory (about 10 minutes)

	Initial	4 th Month	5 th Month	9 th Month	12 th Month	Test Evaluator*	Blinded
	5 hours	4 1/2 hours	3 2/3 hours	4 1/4 hours	4 1/4 hours		
Neurological Exam	√					PI, CoI1	No
Fast Urine Pregnancy	√					N1, N2, N3	No
Shoulder X-Ray	√	√		√	√	PI, CoI3	Yes
Modified Ashworth	√	√	√	√	√	PI, CoI1	Yes
CUE	√	√	√	√	√	T1,T6	Yes
JTHF	√	√	√	√	√	T1,T6	Yes
BB	√	√	√	√	√	T1,T6	Yes
ARA	√	√	√	√	√	T1,T6	Yes
FR	√	√	√	√	√	T1,T6	Yes
ROM	√	√	√	√	√	T1,T6	Yes
Pain NRS	√	√	√	√	√	PI, CoI1, SC2	No
PFTs	√	√	√	√	√	N1, N2, N3	No
ASIA	√	√	√	√	√	PI, CoI1	Yes
Meds Inventory	√	√	√	√	√	PI, CoI1, N1, N2, N3, SC2	No
FES Eval	√					T1,T6	No

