* PI: Principal Investigator, CoI1: Co-Investigator 1, CoI3: Co-Investigator 3, T1-7: Therapist 1-7, N1: Nurse 1, N2: Nurse 2, N3: Nurse 3, SC2: Study Coordinator2.

Table 1: Data Collection Schedule

(2) Intervention:

There are a total of 96 visits: 48 FES assisted intervention visits scheduled 1 hour, 3 times a week for 4 months, and 48 non-FES assisted exercise regimen visits scheduled 1 hour, 3 times a week for 4 months.

3. Blinding, including justification for blinding or not blinding the trial, if applicable.

The evaluator will be blinded to group assignment for the following assessment, but we cannot use true blinding due to the intervention's sensory component:

- c. Severity of gleno-humeral subluxation
- d. Spasticity measurement
- e. Capabilities of the Upper Extremity test
- f. Jebsen-Taylor Hand Function test
- g. Box and Blocks test
- h. Action Research Arm test
- i. Functional Reach test
- j. Range Of Motion of the upper extremity joints
- m. American Spinal Injury Association (ASIA) exam

4. Justification of why participants will not receive routine care or will have current therapy stopped.

All subjects will continue to consistently perform their usual (“baseline”) amount of physical activity throughout the study, including performance of lower extremities assisted FES ergometry, home exercise stretching program, cardiovascular conditioning, etc. “Baseline” activity is defined as amount of physical activity performed for at least 1 month prior to enrollment. Routine care will not be interrupted.

5. Justification for inclusion of a placebo or non-treatment group.

Both groups will receive some type of intervention: upper extremity passive ergometry or FES assisted upper extremity ergometry. This way, the effect of FES application will be extracted.

6. Definition of treatment failure or participant removal criteria.

Treatment failure constitutes of:

- Increased pain (more than 3 points increase on the NRS).
- Increased shoulder subluxation (more than 1 cm).
- Decreased range of motion (more than 15 deg).

Subjects will be removed from the study if they:

- Requires significant hospitalization (that would interfere with physiologic processes proposed to be studied through the protocol, i.e. e-stim) – at the discretion of PI.
- Become pregnant.

7. Description of what happens to participants receiving therapy when study ends or if a participant's participation in the study ends prematurely.

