Accurate and complete study records will be maintained and made available to representatives of the U.S. Army Medical Research and Materiel Command. These representatives are authorized to review research records as part of their responsibility to protect human research volunteers. Research records will be stored in a confidential manner so as to protect the confidentiality of subject information.

XIII. RISK AND INJURY

a. Risks, Risk Management:

All assessments and intervention sessions will be supervised by the Principal Investigator.

For all the study procedures, the risks and risk management are defined in the sections below.

1. Assessment Risks:

a) Neurological Exam: During testing, the subject might experience pain induced by hitting/tapping of the arm, but usually, the sensation experienced is a quick, non-painful touching sensation. To minimize the risk, one of the study team member trained in the procedure will perform the test.

b) Fast Urine Pregnancy Test: There is the possibility of psychological stress occurring if testing shows that the subject may be pregnant. To minimize the risk in the event that pregnancy test results are positive, the result will be disclosed to the subject. If the subject is uncomfortable with this arrangement, his/her consent to participate in this study is not recommended.

c) Severity of gleno-humeral subluxation: The subjects receive ionizing radiation due to the diagnostic bilateral shoulder X-ray procedures they receive at the Initial, 4th Month, 9th Month, and 12th Month visit. The Total Effective Dose from the procedures is 0.4 rem. This is more than the 0.3 rem that the average person in the United States gets each year from natural sources like the sun, outer space, air, food and soil. It is less than the 5 rems of radiation that is allowed each year for people who are exposed to radiation in their jobs. To minimize the risk, pregnant women are excluded from the study.

d) Spasticity Measurement: There is a risk of eliciting spasms during the test. Subjects will feel a quick pull of the muscle, which might be painful at times. To minimize the risk, one of the study team member trained in the procedure will perform the test.

e) Capabilities of the Upper Extremity (CUE) test: There are no known risks associated with this test.

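### The PI is said to supervise every intervention session yet may score three primary outcomes as a blinded evaluator, and the plan does not reconcile the two

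*Combined protocol and SAP*

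**What the plan says.** Section XIII.a opens the risk section with this sentence: "All assessments and intervention sessions will be supervised by the Principal Investigator".

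Table 1 (XI.a.2) gives the evaluators for each test and whether they are blinded. The PI appears with Co-Investigator 3 for the shoulder X-ray, and with Co-Investigator 1 for Modified Ashworth and for ASIA. All three rows are marked blinded. All three measures are among the nine instruments listed in XI.c.1 under the primary outcome; no secondary outcomes are named.

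On blinding, XI.a.3 says: "The evaluator will be blinded to group assignment for the following assessment". Its list includes subluxation, spasticity and ASIA, and XI.c.3 repeats that the evaluator is blinded.

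Group assignment is the order of treatment. Under XI.a.1(2), subjects are randomised "either to group 1, which will first engage in the FES assisted ergometry followed by the non-FES assisted exercise", or to group 2, which takes the reverse order. For the FES period: "Silver mesh self-adhesive surface electrodes will be used to conduct the stimulation". The comparator is strengthening, stretching, splinting and "any other therapeutic interventions that do not use electrical stimulation".

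The nearest thing to a safeguard is in X.b. Research Coordinator 1 manages the password-protected sequence file and has the task: "Assign participants to subgroups according to the randomized sequences".

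**The concern.** Subjects feel the stimulation and cannot be blinded, so the description of the trial as single-blinded rests on the evaluators. If a person who has watched a subject's sessions then grades that subject, the grade can be influenced by expectation.

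The exposure is not equal across the three measures. Modified Ashworth is a 0 to 4 score given by the examiner, and ASIA is a motor and sensory examination conducted by the examiner. Both leave room for judgement. Subluxation is a distance measured on a film, so the risk there is smaller.

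Randomisation and the crossover would not remove such a bias. It would follow the treatment a subject has just had, and so would add to the FES contrast that the trial is meant to estimate.

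**Working it through.** The plan gives no figure to reproduce. The check sets the passages side by side and then counts the assessments exposed.

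**1. Is it the same person?** Yes. The key under Table 1 defines PI as the Principal Investigator, the role named in XIII.a.

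**2. Would a session reveal the assignment?** Yes. Surface electrodes and stimulation belong to the FES period only. XI.a.5 and XI.b.2 describe the control differently, as motor-driven cycling on the same device, but there too stimulation is programmed only for the treatment group. With two sequences and a fixed order within each, one session in either period identifies the sequence for every later assessment.

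**3. Does the custody rule in X.b prevent this?** No. It restricts who sees the list, not what a session supervisor sees being delivered.

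**4. Does the caveat about true blinding in XI.a.3 help?** No. It cites the sensory component of the intervention, which most naturally concerns the subject. It does not explain how an evaluator stays unaware.

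**5. What would literal supervision involve?** XI.a.2(2) states: "There are a total of 96 visits", made up of 48 FES and 48 non-FES visits per subject. For 24 subjects, 24 × 96 = 2304 one-hour sessions.

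**6. How many scorings could be affected?** Inputs are 24 subjects (IX.b) and the visit pattern in Table 1. Baseline precedes the intervention and is left out. The plan names no primary time point, so every post-baseline visit is counted.

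| Measure | Post-baseline visits (months) | Scorings, 24 subjects |
|---|---|---|
| Shoulder X-ray | 4, 9, 12 | 24 × 3 = 72 |
| Modified Ashworth | 4, 5, 9, 12 | 24 × 4 = 96 |
| ASIA | 4, 5, 9, 12 | 24 × 4 = 96 |
| Total | | 72 + 96 + 96 = 264 |

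Of these, 96 + 96 = 192 are Ashworth or ASIA. With the maximum attrition of 4 in IX.b, 20 completers give 20 × (3 + 4 + 4) = 220.

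These are upper limits. Table 1 does not say how scoring is divided between the PI and the co-investigators, so the PI's share may be anything from none to all.

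**The case against.** The best defence is that the conflict turns on one word in a safety section. The XIII.a sentence introduces a list of procedure risks. It also has the PI supervising assessments that Table 1 gives to therapists and nurses, and attendance at 2304 sessions is implausible. General oversight is a natural reading, and it does not by itself show that the PI knows each subject's sequence. Each of the three rows names an alternate, so a PI who has become unblinded can step aside without breaching anything. The protocol's opening pages were not available and may describe staff roles.

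Much of this stands. A reader might infer that nothing stops an unblinded PI from scoring. That is not so: XI.a.3 requires a blinded evaluator for these measures. The rule exists. What is missing is a procedure for keeping it and a supervision clause compatible with it.

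The defence does not dispose of the point. The available text does not define supervision, and full attendance is not needed, because one session per subject is enough. Oversight without attendance can also inform: XVII has the PI reporting on serious events, and the FES risks listed in XIII.a are stimulation-site pain and skin burn. That route reaches only subjects who have a reportable event.

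**Conclusion.** The point holds as an unreconciled conflict that should be fixed. If supervision includes attending sessions, XIII.a and the PI entries in Table 1 cannot both be followed while keeping the blind required by XI.a.3 and XI.c.3. If it means oversight only, the protocol needs to say so.

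The extent is 3 of 9 primary instruments and between 0 and 264 post-baseline scorings. The upper end assumes that all 24 subjects complete, that the PI has seen a first-period session of each before month 4, and that the PI does all the scoring. The size of any bias cannot be derived from the documents. Confidence is medium, because the meaning of supervision is open and the opening pages were not seen.

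Two stronger readings should be resisted:

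- A reader might infer that the blind is in fact broken. The documents do not show that the PI attends sessions or does the scoring.
- A reader might infer that Co-Investigator 1 is also unblinded, being listed for pain NRS and among the medication inventory staff ("PI, CoI1, N1, N2, N3, SC2"), both marked not blinded. That marking means only that no blinding is claimed for those tests. It does not show that Co-Investigator 1 knows the allocation.

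**What to change.** 1. **Table 1.** Remove the PI as evaluator for shoulder X-ray, Modified Ashworth and ASIA. This leaves Co-Investigator 3 for films and Co-Investigator 1 for the two examinations. First confirm that neither attends or delivers intervention sessions; if either does, name another evaluator for that row.
2. **XI.a.3.** State that whoever scores a blinded outcome does not attend, supervise or deliver that subject's sessions and is not told the allocation, and that subjects are asked not to disclose it.
3. **XIII.a.** State that PI supervision is safety oversight, and that the PI neither scores nor takes part in scoring the blinded outcomes. Removing the PI from Table 1 alone would still leave the PI supervising the blinded assessments.

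As an optional precaution, pain NRS and the medication inventory can go to other staff already listed for them: Study Coordinator 2 for NRS, and the nurses or Study Coordinator 2 for medications.

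The cost is three text edits, one evaluator per measure, no backup if that evaluator becomes unblinded, and tighter scheduling. Using the test times in XI.a.2 and counting baseline, Co-Investigator 1 would carry up to 24 × 5 × (15 + 60) min = 9000 min, or 150 hours. Co-Investigator 3 would read up to 24 × 4 = 96 bilateral film sets. These are total loads; the increase over current practice is unknown because the present split is not stated.

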Appendix: Study Related Documents

XXI. Appendix: Study Related Documents

a. Recruitment forms:

Subject Recruitment Flyer: File is “14481 Subject Recruitment Flyer 2010-09-07.docx”

ICSCI Newsletter language: File is “14481 Newsletter language 2010-09-07.docx”

KKI Facebook page language: File is “14481 KKI Facebook language 2001-03-24.docx”

KKI On-Hold phone message: File is “14481 KKI On-Hold Message 2011-03-23.docx”

KKI Press Release: File is “ICSCI DoD Research Release 2011-June.docx”

Waiver of privacy authorization from the IRB on Record: File is “14481 HIPAA Form4 2010-09-07.docx”

Medical Chart Review Form: File is “14481 Medical Chart Review Form 2010-09-07.docx”

Phone Screening Form: File is “14481 Phone Screening Form 2010-09-07.docx”

Inc/Exclusion Criteria Index Card: File is “14481 Index Card 2010-09-03.docx”

Inc/Exclusion Wall Index: File is “14481 Wall Listing 2010-09-03.docx”

Cover letter: File is “14481 Inclusion-Exclusion guide 2010-09-07.docx”

b. Informed Consent forms:

File is “14481 Consent Form 2011-06-10.docx”

c. Case Report Forms:

File is “14481 Case Report Form 2011-03-24.docx”

File is “14481 Test 0 Screening Form 2008-09-15.doc”

File is “14481 Test 1 Subluxation 2009-05-01.doc”

File is “14481 Test 2 Modified Ashworth 2009-05-01.doc”

File is “14481 Test 3 CUE 2009-05-01.doc”

File is “14481 Test 4 Jebsen-Taylor 2009-05-01.doc”

File is “14481 Test 5 Box & Blocks 2009-05-01.doc”

File is “14481 Test 6 ROM 2009-05-01.doc”

File is “14481 Test 7 NRS 2009-05-01.doc”

File is “14481 Test 8 ASIA 2009-05-01.doc”

File is “14481 Test 9 Meds 2009-05-01.doc”

File is “14481 Test 10 Functional Reach 2009-05-01.doc”

File is “14481 Test 11 PFTs 2009-05-01.doc”

File is “14481 Test 12 ARAT 2010-01-15.doc”

File is “14481 Test 13 FES Eval 2010-02-18.doc”

File is “14481 Payment Form 2010-08-16.docx”

d. Serious Adverse Event report forms:

Any adverse event is reported to the IRB of record electronically as a Further Study Action(FSA), using the local IRB of Record website (<https://e-irb.jhmi.edu>).

The report will be printed and forwarded to the ORP HRPO as described in section 0. of this protocol. A template of the IRB Problem/Event Report Form is provided.

File is “IRB Problem Event Report Form Template.pdf”

Protocol No. ERMS # 08284002, Local IRB:NA_00014481.

Principal Investigator: [name], M.D.

Appendix: Medical Device Related Documents

XXII. Appendix: Medical Device Related Documents

The device is FDA cleared under section 510(k). The device, RT300-SLSA, clearance number is K072398.
File is “*K072398.pdf*”
